3.5.2 Secondary Efficacy Endpoints and Analyses

3.5.2.1 Secondary efficacy endpoints

The secondary efficacy endpoints are as follows:

• Change from baseline in ESSPRI at Day 169 (population #1)

• Proportion of subjects achieving ESSDAI[3] and ESSDAI[4] response, defined as a decrease of at least 3[4] points from baseline in the ESSDAI at Day 169 without premature discontinuation from the study and without receiving rescue medications (population #1)

• Proportion of subjects achieving ESSPRI response, defined as ≥ 1 point or 15% reduction from baseline in ESSPRI score at Day 169 without premature discontinuation from the study and without receiving rescue medications (population #2)

- Change from baseline in FACIT-Fatigue score at Day 169 (population #1 and #2)
- Change from baseline in OSDI at Day 169 (population #1 and #2)
- Change from baseline in PGIS at Day 169 (population #1 and #2)

FACIT-Fatigue:

The FACIT-Fatigue is a 13-item questionnaire, subject-completed, used to assess the impact of fatigue. Its recall period is 7 days. The responses range from 0 (Not at all) to 4 (Very Much). To calculate the total score, the negatively stated items are reversed by subtracting the response from "4". Final scores are the sum of the responses and range from 0 to 52. Higher scores indicate better quality of life.

OSDI:

OSDI is a valid and reliable instrument for assessing effect on vision-related function and dry eye disease severity (normal, mild, moderate, and severe). Its recall period is 1 week. It is composed of 12 questions that the physician asks the subject and circles the number that best represents each question. The responses for each question range from 0 (None of the time) to 4 (All of the time). The OSDI score is calculated as follows:

OSDI score = (sum of scores for questions answered) / (number of questions answered) \times 25

The OSDI score ranges from 0 to 100 with higher scores signifying greater disability.

PGIS:

The PGIS is a single item designed to capture the subject's perception of overall symptom severity over the past week on a 5-point categorical response scale (none, mild, moderate, severe, very severe).

3.5.2.2 Secondary efficacy analysis

The continuous secondary efficacy endpoints of population #1 and population #2 will be analyzed based on Stage I data for the full analysis set using the MMRM approach, with treatment, visit, visit by treatment interaction, randomization stratification factor, and corresponding baseline value. Handling plan for the rescue medication use and treatment discontinuation will be the same as those described for the primary endpoints in sections 3.5.1.3 and 3.5.1.5.

The details of these analyses and presentations of results will be the same as those described for the primary endpoints in section 3.5.1.2.

The analysis for Stage II + Off-treatment follow-up period will be performed using the same MMRM approach based on the cross-over analysis set. Data collected after rescue medications and after discontinuation of study treatment will be included.

The binary secondary efficacy endpoints of population #1 and population #2 will be analyzed for the full analysis set using a logistic regression model, with treatment and corresponding baseline score included in the model.

The estimated treatment effect (ie, the odds ratio for VIB4920 versus placebo), corresponding 90% CI, and 2-sided p-value will be presented. In addition, the response rate and the corresponding 90% CI within each treatment group will be presented. Longitudinal presentations of results over time up to Day 169 will be created using full analysis set. In addition, the analysis will be produced for Stage II + Off-treatment follow-up period separately using the cross-over analysis set.

3.5.3 Exploratory Efficacy Endpoints and Analyses

3.5.3.1 Exploratory efficacy endpoints

The exploratory efficacy endpoints are as follows:

3.5.4 Handling missing items of clinical outcome assessments (COAs)

The ESSDAI is a clinician reported outcome. There will be very few missing items expected. All PROs will be administered by ePRO. Questions are mandatory so there will be no skipped items. But in case there are missing items, the following algorithms will be used to handle the missing items.

3.5.4.1 ESSDAI and ESSPRI

If less than 50% of items are missing, the missing individual items are imputed using last observation carry forward (LOCF) approach before calculation of total score. The total score will not be calculated and will be treated as missing if 50% or more of items are missing.

3.5.4.2 FACIT-Fatigue

The missing items will be handled according to FACIT scoring guidelines. If less than 50% of items are missing, the total scores will be calculated as follows:

Total score = (Sum of scores for items answered) / (N of items answered) $\times 13$

The total score will not be calculated and will be treated as missing if 50% or more of items are missing.

3.5.5 Explore clinically meaningful within-subject change score of COAs

The anchor-based methods supplemented with both empirical cumulative distribution function (eCDF) and probability density function (PDF) will be used to explore the clinically meaningful within-subject change score of COAs. The eCDFs display a continuous view of the score change (both positive and negative) in the COA endpoint from baseline to the proposed time point on the X-axis (horizontal axis), with the Y-axis (vertical axis) representing the cumulative proportion of subjects experiencing up to that level of score change.

The receiver operating characteristic (ROC) curve analysis will be used as supportive approach to explore the clinically meaningful within-subject change score.

Spearman's correlation analyses will be used to examine the strength and magnitude of relationship between the COA measures and potential anchors. The threshold for consideration as an anchor will be a correlation coefficient > 0.30.

3.5.5.1 ESSDAI

The clinically meaningful within-subject change score of ESSDAI will be explored for population #1 based on the pooled data across treatment groups. The anchor measures for ESSDAI are PGIS, **Sector 1999**. The eCDF curve of change from baseline to Day 169 in ESSDAI will be plotted for each distinct anchor category as defined and identified by the anchor measures. A potential range for the meaningful change can be derived from eCDF plots (e.g., using median change, 25th percentile change, 75th percentile change).

•

• PGIS and ≥ 2 category decrease, 1 category decrease, no change, 1 category increase, and ≥ 2 category increase

The PDF curves of change from baseline to Day 169 in ESSDAI will also be plotted for each distinct anchor category to aid the interpretation of eCDF curves.

The eCDF curve of change from baseline to Day 169 in ESSDAI will also be plotted by each treatment group without separating into distinct anchor category.

The ROC curve analysis will be performed using logistic regression model with anchor as binary outcome and change from baseline to Day 169 in ESSDAI score as quantitative predictor. The score that best distinguishes levels of the anchor as listed below (based on sensitivity and specificity) will be identified.

- •
- PGIS and ≥ 2 category decrease, ≥ 1 category decrease

3.5.5.2 ESSPRI

The clinically meaningful within-subject change score of ESSPRI will be explored for population #1 and population #2 based on the pooled data across treatment groups within each population. The anchor measures for ESSPRI are PGIS and the eCDF and PDF curves of change from baseline to Day 169 in ESSPRI will be plotted the same way as that for ESSDAI. The ROC curve analysis will be performed as well.

3.6 Safety Analysis

3.6.1 Adverse Events

In general, if an AE onset is on or after the first dose of IP administration, the AE will be considered as a TEAE. Otherwise, the AE will be considered as a non-treatment emergent AE.

The AEs will be summarized for different study periods as defined in the Table 3.

Study Period	Inclusion of AEs for Summary
Stage I (Safety analysis set)	Include AEs with an onset on or after the first dose of IP in Stage I up to the time prior to the first dose of IP in Stage II (Day 169) for subjects entering Stage II, and AEs with an onset on or after the first dose of IP in Stage I for subjects not entering Stage II.
Stage II + Off-treatment follow-up (Cross-over analysis set)	Include AEs with an onset on or after the first dose of IP in Stage II (Day 169).
Any VIB4920 exposure (Any VIB4920 analysis set)	Include AEs with onset on or after the first VIB4920 dose (either Stage I or Stage II)

Table 3	TEAEs for different study periods
---------	--

An overall summary table will be showing the number and percentage of subjects with at least 1 event in any of the following categories: TEAE, TESAE, TEAE with outcome of death, TEAE leading to discontinuation of IP, grade 3 or higher TEAE, serious and/or grade 3 or higher TEAE, IP related TEAE, IP related TESAE.

AEs will be coded using the most recent version of MedDRA. All TEAEs will be summarized overall and by MedDRA SOC and PT, by severity and by relationship to IP. Specific AEs will be counted once for each subject for calculating rates, but all events will be presented in subject listings. In addition, if the same AE occurs multiple times within a particular subject, the highest severity and level of causality will be reported. The TEAEs, TESAEs, TEAEs resulting in death, TEAEs leading to discontinuation of IP, Grade 3 or higher TEAEs, IP related TEAEs, and IP related TESAEs will be summarized by SOC and PT. TESAEs will be summarized by SAE criteria as well. In addition, a summary of TEAEs sorted by frequency will be presented by PT.

An AESI is one of scientific and medical interest specific to understanding of the IP. AESIs for this protocol include:

- Thrombotic and embolic events
- Hepatic function abnormality (meeting the definition of Hy's Law)
- Anaphylaxis and clinically significant (Grade 3 or higher) hypersensitivity reactions

• Severe Infusion-related reactions (common terminology criteria for adverse event (CTCAE) Grade 3 or higher)

- Malignant neoplasm
- Immune complex disease
- Infections:
 - Clinically significant (Grade 3 or higher)
 - Opportunistic infections including but not limited to reactivation of latent viral infection, invasive fungal infections, and TB

TEAESIs will be summarized by SOC and PT.

Listings will be provided for all TEAEs and non-treatment emergent AEs.

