8.4 Adverse Events of Special Interest

An AESI is one of scientific and medical interest specific to understanding of the IP and may require close monitoring and collection of additional information by the Investigator. An AESI may be serious or nonserious. The rapid reporting of AESIs allows ongoing surveillance of these events in order to characterize and understand them in association with the use of this IP.

The following AESIs will be particularly monitored in this study (see the Safety Handling Plan for instructions and timing on completing any additional information required for specific types of events related to the categories noted below):

- Thrombotic and embolic events
- Hepatic function abnormality (meeting the definition of HL) (see Appendix 3) for details)
- Anaphylaxis and clinically significant (Grade 3 or higher) hypersensitivity reactions (see Appendix 2 for guidance on diagnosis of anaphylaxis reactions)
- Severe Infusion-related reactions (Common Terminology Criteria for Adverse Events (CTCAE) Grade 3 or higher).

Severity will be assessed according to CTCAE v5

- Grade 1: Mild transient reaction; infusion interruption not indicated; intervention not indicated.
- Grade 2: Therapy or infusion interruption indicated but responds promptly to symptomatic treatment (eg, antihistamines, NSAIDS, narcotics, IV fluids); prophylactic medications indicated for ≤ 24 hours
- Grade 3: Prolonged (eg, not rapidly responsive to symptomatic medication and/or brief interruption of infusion); recurrence of symptoms following initial improvement; hospitalization indicated for clinical sequelae
- Grade 4: Life-threatening consequences; urgent intervention indicated
- Malignant neoplasm
- Immune complex disease
- Infections:
 - Clinically significant (Grade 3 or higher)
 - Opportunistic infections including but not limited to reactivation of latent viral infection, invasive fungal infections, and TB

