10.5.5 Safety Analysis

10.5.5.1 Adverse Events

The AEs will be summarized descriptively for each population. AEs will be coded using the Medical Dictionary for Regulatory Activities by system organ class (SOC) and preferred term (PT). The number and percentage of subjects reporting TEAEs with onset on or after the start of the first infusion of IP will be summarized for each treatment group by SOC and PTs, by severity, and by relationship to the IP. The number and percentage of subjects reporting TESAEs and AESIs will also be summarized.

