2 STUDY OVERVIEW

2.1 Study Objectives and Endpoints

The objectives and corresponding endpoints are listed in Table 1 below:

Primary objective	Endpoints/variables	
• Population #1: To evaluate the clinical efficacy of multiple doses of VIB4920 in glandular and extraglandular manifestations of SS patients with moderate to high systemic disease activity	• Population #1: Change from baseline in ESSDAI at Day 169	
• Population #2: To evaluate the clinical efficacy of multiple doses of VIB4920 in the key subjective complaints of SS (dryness, fatigue, pain)	• Population #2: Change from baseline in ESSPRI at Day 169	
Secondary objectives	Endpoints/variables	
 Population #1: To evaluate the effect of VIB4920 on systemic activity and patient-reported outcomes in subjects with SS 	 ESSPRI ESSDAI[3] and ESSDAI[4] response Functional Assessment of Chronic Illness Therapy (FACIT)-Fatigue Ocular Surface Disease Index (OSDI) Patient's Global Impression of Severity (PGIS) 	
• Population #2: To evaluate the effect of VIB4920 on patient-reported outcomes in subjects with SS	 ESSPRI response FACIT-Fatigue OSDI PGIS 	
• Population #1 & #2: To evaluate the safety and tolerability of multiple doses of VIB4920 in subjects with SS	• Incidence of treatment emergent adverse events (TEAEs), TE serious adverse events (TESAEs), TE adverse events of special interest (TEAESIs), and laboratory, vital sign, and electrocardiogram (ECG) abnormalities	

Table 1	Study	Objectives	and Endpoints
---------	-------	------------	---------------

Table 1Study Objectives and Endpoints

• Population #1 & #2: To characterize the pharmacokinetics (PK) of VIB4920 in subjects with SS	• Drug concentration and PK parameters
• Population #1 & #2: To assess the immunogenicity of VIB4920 in subjects with SS	• Anti-drug antibodies (ADA)
Exploratory objectives (Population #1 & #2)	Endpoints/variables

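### AESIs are defined as seven medical categories but tabulated only by SOC and PT, so no once-per-subject incidence is planned for any single category

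*SAP*

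**What the plan says.** Protocol 8.4 introduces the list with "The following AESIs will be particularly monitored in this study" and names seven categories:

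1. thrombotic and embolic events
2. hepatic abnormality meeting Hy's Law
3. anaphylaxis and Grade 3 or higher hypersensitivity
4. Grade 3 or higher infusion-related reactions
5. malignant neoplasm
6. immune complex disease
7. infections, either Grade 3 or higher or opportunistic

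SAP 3.6.1 repeats the list, starting with "Thrombotic and embolic events". SAP 2.1 and Protocol 3.3.2 and 3.4.2 make AESI incidence part of a secondary safety endpoint in each population.

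On analysis there are four statements.

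- Protocol 10.5.5.1: "The number and percentage of subjects reporting TESAEs and AESIs will also be summarized".
- SAP 3.6.1, the AESI table: "TEAESIs will be summarized by SOC and PT".
- SAP 3.6.1, the overall table: "An overall summary table will be showing the number and percentage of subjects with at least 1 event in any of the following categories". The list that follows begins "TEAE, TESAE, TEAE with outcome of death, TEAE leading to discontinuation of IP, grade 3 or higher TEAE" and goes on to serious and/or Grade 3 or higher events and to IP-related TEAEs and TESAEs. That makes eight rows, none of them for AESIs.
- SAP 3.6.1, the counting rule: "Specific AEs will be counted once for each subject for calculating rates". It works at the level of the specific event. There is no matching rule for an AESI category.

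**The concern.** The seven categories are the safety questions that the sponsor chose to ask. A SOC and PT table answers a different question, because MedDRA groups terms by organ class. A category whose events can arise in several organs is spread over several rows. A subject with events in two of those rows appears in both, so adding the rows does not give the number of affected subjects.

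The category most exposed is the one listed first. Thromboembolism also underlies exclusion criteria 1 to 3 in both populations, and coagulation tests are scheduled at every treatment and off-treatment visit (Protocol 8.5.4). A reader of the study report will want the proportion of subjects per group with at least one thrombotic or embolic event, and the plan does not provide for that figure.

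The infection category has a second problem. Its two criteria, Grade 3 or higher and opportunistic, are not separated in an AESI table arranged by SOC and PT.

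**Working it through.** The documents state no figure on this point, so there is none to reproduce. The check sets the texts side by side and then illustrates the effect under stated assumptions.

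**Step 1. What is planned for each quantity.**

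| Quantity | Protocol 10.5.5.1 | SAP 3.6.1 |
|---|---|---|
| Subjects with any AESI | Yes | No row in the overall summary |
| Subjects per AESI category, each counted once | No | No |
| AESIs by SOC and PT | Not mentioned | Yes |
| Which terms make up a category | No | No |

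SAP 3.6.1 does use an axis outside MedDRA elsewhere: serious events are also summarized by seriousness criterion. AESIs have no such additional axis.

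**Step 2. Why rows cannot be added.** Let a category fall in k rows with r1, ..., rk affected subjects. The number of distinct subjects D satisfies

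max(r1, ..., rk) ≤ D ≤ r1 + ... + rk.

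Hypothetical example: 36 VIB4920 subjects (the planned group size in Population #1) and four rows with one subject each. Each row shows 1/36 = 2.8%. D lies between 1 and 4, so the category incidence lies between 1/36 = 2.8% and 4/36 = 11.1%. At the upper end the Clopper-Pearson 95% interval is 3.1% to 26.1%. The planned table looks the same in every case. The four events and the four rows are assumptions. No document gives such a rate, and Protocol 2.1.4.1 reports no thromboembolic events in the single-dose study.

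**Step 3. How often a cluster shows.** Assume a true category risk q of 2%, 3% or 5%, split evenly over four organ classes. The chance of at least two affected subjects among N is

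P = 1 − (1 − q)^N − N·q·(1 − q)^(N−1),

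with q/4 in place of q for one given organ class. N is the planned VIB4920 group: 36 (Population #1), 51 (Population #2), and 36 + 51 = 87 for both together.

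| N | Whole category, q = 2% / 3% / 5% | One given organ class |
|---|---|---|
| 36 | 0.162 / 0.294 / 0.543 | 0.014 / 0.030 / 0.074 |
| 51 | 0.272 / 0.455 / 0.731 | 0.027 / 0.056 / 0.134 |
| 87 | 0.521 / 0.739 / 0.936 | 0.071 / 0.139 / 0.297 |

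Protocol 10.5.5.1 plans AE summaries for each population, so the first two rows are the relevant ones; N = 87 is for orientation only. The last column refers to one named organ class, not to any of the four. The risks and the even split are assumptions and are not taken from the documents.

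**The case against.** The strongest reply is that this is a matter of presentation. Much of that stands.

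- **The endpoint is aggregate.** It is the incidence of AESIs, not of each category, and Protocol 10.5.5.1 commits to that count. A reader might infer that a secondary endpoint has no planned analysis. That does not follow: the aggregate is planned in the protocol, and the SAP merely fails to carry it into its overall table. Only the category breakdown is unplanned.
- **The counts can be recovered.** SAP 3.6.1 plans listings of all TEAEs. The statistical programming plan (SAP 3.1.2 and 3.4.4) and the Safety Handling Plan (Protocol 8.4) were not supplied and may say more. A reader might infer that category incidence will never be calculated. The documents show only that the protocol and SAP do not plan it.
- **A signal would not necessarily be lost.** The planned table is restricted to AESIs, so thrombotic terms would not be buried among all TEAEs. Protocol 8.4 provides for rapid AESI reporting, and Protocol 12.1 for independent safety review. The documents do not support a claim that a thromboembolic cluster would go unseen.
- **Not every category is split.** The documents do not show how terms code. Malignancy and infection probably stay largely within one organ class, where the SOC row would come close to a category count. SAP 3.6.1 also plans a table of Grade 3 or higher TEAEs, which should show most severe infections; the opportunistic subset is then what remains without a count.
- **Infusion-related and hypersensitivity reactions are separate categories.** A difference in coding between them splits nothing and is no evidence here.

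What remains is that the SAP states a tabulation rule which, followed as written, gives no valid subject count for a category crossing organ classes. Nor do the supplied documents say which terms belong to a category.

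**Conclusion.** The point holds as a gap in safety reporting. Seven AESI categories are defined, none has a planned once-per-subject incidence in the supplied documents, and the SAP overall summary omits even the any-AESI count that the protocol promises. The gap matters mainly for thrombotic and embolic events, hypersensitivity and immune complex disease, and for telling opportunistic from Grade 3 or higher infections within the AESI table.

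Its size depends on coding and on event numbers that the documents do not give. The range of 2.8% to 11.1% for one and the same table is an illustration. It rests on the general fact that MedDRA groups terms by organ class and on an assumed four rows. No estimate, test, analysis set or data collection changes, and the primary efficacy analyses are unaffected. This is a cheap improvement, not a flaw in the design.

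**What to change.** In SAP 3.6.1, replace the AESI sentence with: *TEAESIs will be tabulated by the AESI categories listed above, with each subject counted once per category, and by SOC and PT within category.* Show the two infection criteria as separate lines under infections. Add a row for any TEAESI to the overall summary table, which also brings the SAP into line with Protocol 10.5.5.1. Use the study periods of SAP Table 3.

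Fix the assignment of events to categories before the interim unblinding, for example with a medically reviewed term list, so that membership is not chosen after results are seen. The documents mention no AESI flag on the eCRF, so its existence should not be assumed. Exact confidence intervals are optional; the SAP plans none for its other AE tables.

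The cost is one sentence, one extra table, one extra row and the medical work of making the list. Nothing changes for sites or subjects.

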3.6.2 Clinical Laboratory Evaluation

The hematology, coagulation, serum chemistry, urinalysis, and immunoglobulins parameters, as well as changes from baseline, will be summarized with descriptive statistics at each visit. Shift from the baseline relative to the normal range will also be summarized. Additionally, worst toxicity grade, ≥grade 3 toxicity post-baseline, and shift from baseline to worst toxicity grade in hematology, coagulation and serum chemistry parameter will be produced. The summary of clinical laboratory data will be generated for Stage I and Stage II + Off-treatment follow-up period separately based on the safety analysis set and cross-over analysis set respectively.

